This analysis approach takes account of potential imbalance between the implementation and comparator areas. In each country, surveillance for meningitis and severe malaria will be maintained in a subset of clusters, through selected hospitals. Each hospital draws patients primarily from a small number of clusters. These clusters may not be well balanced between intervention and comparator with respect to population size, the underlying risk of meningitis or malaria, access to hospital, and the diagnostic performance of the hospital. For mortality, although a larger number of clusters has been randomized, there is also a risk of imbalance if it is not possible to implement surveillance uniformly well in all clusters. Pre-intervention data on these outcomes is not available as surveillance was established for the purpose of the evaluation, at the same time as the vaccine was introduced.

Methods for estimating rate ratios and rate differences are detailed below.

Assumptions of the analysis approach:

The approach assumes that:

- a) the incidence by age is such that there are expected to be enough cases for analysis (in both group B and group A)
- b) the age of cases will be determined sufficiently accurately to assign them to group A or B reliably
- c) there is limited catch-up vaccination, so that a group can be defined based on age who would not have received RTS,S vaccine

d) for rate ratios, we have assumed that the ratio of person time between Group A and group B is the same in each cluster and in both intervention and comparator areas although this assumption could be relaxed if cluster-specific data were available. The population size of the cluster does not need to be known to estimate rate ratios, but for rate differences, population denominators are needed. For both effect measures an assumption is that the ratio of incidence of the outcome of interest between eligible and non-eligible age groups, would be the same in implementation and comparison areas in the absence of the malaria vaccine. We would expect this to hold for other conditions, this could be checked by comparing incidence ratios of outcomes unrelated to malaria. Such “tracer” conditions could then be used to adjust for an imbalance, by comparing the ratio (eligible:non-eligible) for the outcome of interest to the corresponding ratio for the tracer conditions, and comparing this double ratio between implementation and comparator areas.

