(average for the period from vaccine introduction to Dec 2020), and estimates of the degree of contamination (% admissions (or % deaths) in vaccine-eligible age groups in comparator areas, who had received RTSS-1).

Country	Coverage of RTSS-1	Contamination (RTSS-1 coverage in comparator areas in hospital catchments)	
		from mortality surveillance (HBR or recall)	from hospital admissions (HBR or recall)
Malawi	72.3%	4.8%	2.7%
Ghana	69.0%	0.0%	5.9%
Kenya	79.8%	5.3%	4.6%
TOTAL	73.7%	3.4%	4.4%

Table 5: Power to detect or exclude effects on safety outcomes, of the magnitude observed in the phase 3 trial, and power to detect impact on hospital admission with severe malaria, and on all-cause mortality

	Effect in the phase3 trial ¹	Corresponding effect size, allowing for coverage ²	Effect size allowing for contamination ³	Effect size allowing for confounding ⁴	Number of events required for given power to detect or exclude effects of the given size ⁵	
					90% power	80% power
Safety outcomes:						
Meningitis	10.5	8.00	5.80	5.66	90	70
Cerebral malaria	2.57	2.16	2.03		400	300
Gender interaction (mortality)	1.7	1.52	1.47		2000	1500
Impact:						
Severe malaria ⁶	0.66	0.75	0.76		4000	3000
Mortality ⁷ a)	0.898	0.92	0.93		24000	18000
b)	0.864	0.90	0.90		17600	13100

1 In the phase 3 trial, the observed rate ratio for meningitis (RTS,S/AS01:control) was 10.5, and for cerebral malaria, 2.57. Among girls, there was a higher mortality rate in RTS,S/AS01 recipients than controls, the mortality ratio was 2 over the whole trial period, and was 1.7 in the first part of the trial (from enrolment until the 4th dose was administered) and 3.4 in the latter part of the trial.

2 Assuming coverage of RTSS-1 of 74% (the average value in Table 4)

3 Assuming coverage of RTSS-1 in comparator areas is 4%

4 Confounding: For meningitis, assuming RTSS-recipients more likely to have received other vaccines that would prevent meningitis (90% coverage of anti-meningitis vaccines, 50% efficacy against all-cause meningitis, all RTSS recipients have received anti-meningitis vaccine). Based on preliminary data from baseline surveys, EPI coverage did not appear to differ between high and low malaria prevalence areas, and was similar in children who tested positive for malaria infection by RDT and children who tested negative. We have therefore assumed no confounding for impact outcomes.

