5 The number of events required for given power. The numbers refer to the total events in eligible and non-eligible groups combined, except for the interaction by gender, where the number refers to the number of deaths in vaccine-eligible ages.

[figure not shown]
6 Efficacy of RTS,S/AS01 against severe malaria, during the first 20 months of the trial (ITT analysis) was 34% (rate ratio 0.66).

7 The expected reduction in all-cause mortality is a) 10.2%, if efficacy against malaria deaths is 34%, and the percentage of deaths caused by malaria (in the absence of the vaccine) is 30%. This translates to a 7% reduction after allowing for 74% coverage and 4% contamination. If the percentage of deaths caused by malaria is 40% (b), the expected reduction in all-cause deaths is 14%, which translates to a 10% reduction at population level.

Further details of power simulations, including predicted distribution of point estimates of effects, are given in Annex 4. Based on incidence rates of the key outcomes observed during the first 12 months of surveillance, we estimated that by the end of month 24 (April 2021), sufficient events would be expected to have accrued to give 90% power to detect or exclude a 5-fold increase in incidence of hospital admission with meningitis associated with introduction of RTS,S/AS01, and at least 80% power to detect a 2-fold increase in incidence of hospital admission with cerebral malaria, and 90% power to detect a 1.4-fold relative increase in all-cause mortality in girls compared to boys associated with RTS,S/AS01 introduction, in pooled analysis across the three countries. By this time point, there would also be good power to detect a reduction in the incidence of hospital admission with severe malaria. There would be low power to detect reductions in all-cause mortality at this time point, but it is anticipated that sufficient events would have accrued by the end of the evaluation (month 46 in each country) to have 90% power to detect a reduction of 10% and 80% power to detect a reduction of 8%.

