Data will be reviewed by the DSMB at 6-monthly intervals. If there is evidence of increased incidence of safety outcomes in implementation clusters in vaccine-eligible age groups, vaccination status of cases in these groups would be examined, to determine if the proportion vaccinated is consistent with an excess given the level of vaccine coverage from administrative data; sensitivity analysis would be done to explore effects on results of uncertainties in age, missing data, and alternative case definitions; incidence of all cause admissions and admissions for conditions unrelated to the vaccine, would be compared between implementation and comparator areas to understand potential biases; and analysis will be done to determine if the results are similar in all three countries. If after completing these analyses, the data are consistent with an increased risk of adverse outcomes associated with RTS,S introduction, there will be an assessment of the magnitude of the excess risk in relation to evidence on potential benefits, to decide whether to recommend suspending or discontinuing vaccination.

Final analyses will be done when data up to month 46 are complete in all countries. Figure shows the accrual of person time, in the three countries combined, during the evaluation. During the latter half of the evaluation the total person time increases by a factor of more than 4.

9. Rebound effects

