- % children who received RTS,S4 who had previously received less than 3 doses of RTS,S.

18. Other interventions that might affect MVPE outcomes

A diary of other interventions (e.g. LLIN distribution, IRS campaigns, azithromycin MDA, expansion of community case management, creation of new health facilities) maintained for each cluster would allow reporting of contextual information about the possible influence of other interventions taking place in study clusters during the MVIP. These are being recorded by the evaluation partners and reported to WHO as part of quarterly technical reports. Likewise, the PATH and WHO MVIP team members in each pilot country records similar events that can affect EPI delivery of the RTS,S vaccine.

19. Calculation of rate ratios and rate differences

Incidence of the primary safety outcomes (probable meningitis, confirmed meningitis, cerebral malaria) and impact outcomes (deaths, deaths excluding injuries, and severe malaria) will be compared between comparator and RTS,S areas, in each country and for the three countries combined. For mortality, the evaluation is powered to estimate effects within each country by the end of the 46 months. For meningitis, primary analysis will be pooled across the three countries.

Rate ratios and rate differences, with 95% and 99% confidence intervals, will be calculated as in the table below. Secondary safety and impact outcomes listed in Table 5 will be analysed in the same way.

Table 8: Dummy table for effect measures for safety and impact outcomes

Outcome	Analysis populations* primary (secondary)	Comparator N/PYAR rate	RTS,S N/PYAR rate	Rate ratio (95%CI)	Rate difference (95%CI)
Safety:					
Probable meningitis	A1 (A4)				
Confirmed meningitis	A1 (A4)				
Cerebral malaria	A1 (A4)				
Impact:					
Deaths	A2 (A4)				
Deaths (excl. injury)	A2 (A4)				
Severe malaria	A2 (A4)				

*A1: eligible for RTS,S; A2: eligible for 3 doses of RTS,S; A4: received 3 doses of pentavalent vaccine

(Note: For severe malaria, if a reduction in the number of admissions for all-cause febrile illness is observed that is commensurate with the reduction in severe malaria, this would give reassurance that the reduction in severe malaria was not caused simply by a reduction in the prevalence of parasitaemia without prevention of severe illness.)

Subgroup analyses

Gender

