(We could have calculated the ratios within each cluster and then compared the mean or geometric mean between the two arms, this would give equal weight to each cluster (and there would need to be an adjustment to allow for clusters with zero events in group B). The approach we will use for the MVPE weights clusters according to their population).

The variance of R_j is [23,22]:

$$V(R_j) = \left(\frac{m_j}{(m_j-1)n_{j,B}^2} \right) \sum_{i=1}^{m_j} (n_{j,i,A} - R_j n_{j,i,B})^2 \quad j = 0,1$$

where m_j is the number of clusters in arm j , R_j is the point estimate of the rate ratio in area j , and $n_{j,i,A}$ and $n_{j,i,B}$ is the number of events in group A in cluster i in area j and $n_{j,i,B}$ is the number of events in group B in cluster i in area j , and $n_{j,B}$ the total events in group B in area j .

The log rate ratio comparing the RTS,S and comparator areas is

$$D = \log(R_1) - \log(R_0), \text{ with variance } V(D) = V(R_1)/R_1^2 + V(R_0)/R_0^2.$$

We will have an estimate of D for each country, D_1 , D_2 and D_3 , the combined estimate is then

$$D_{\text{combined}} = \sum D_i / V(D_i) / \sum 1/V(D_i), \quad i=1..3, \text{ and the variance is } V(D_{\text{combined}}) = 1 / \sum [1/V(D_i)].$$

To test for interaction by country (Cochran's Q test), $\sum [(D_{\text{combined}} - D_i)/V(D_i)]^2$ is referred to the X^2 distribution with 2 degrees of freedom [24].

The final rate ratio is given by $\exp(D_{\text{combined}})$ and the $100(1-\alpha)\%$ confidence interval by

$$\exp[D_{\text{combined}} \pm t_{\alpha/2, C-6} \sqrt{V(D_{\text{combined}})}], \text{ with df equal to the total number of clusters } C \text{ less } 2 \times 3 = 6.$$

This final stratified rate ratio represents *the average increase or decrease in incidence of the outcome due to introduction of RTS,S vaccine, in the age group of children eligible to receive the vaccine, across all three countries*. As for the rate differences, the estimated value will depend on the analysis population chosen (A1, eligible for RTS,S; A2 eligible for 3 doses of RTS,S; or A3 eligible for 3 doses and followed up to 39 months of age) and the time point when analysis is done.

It is not planned to adjust for cluster-level covariates. (The baseline surveys are not designed to produce accurate estimates of malaria transmission and other indicators for individual clusters). We will adjust analyses of impact for transmission strata, in a secondary analysis.

Gender interaction

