area	cluster	na	ya	nb	yb	area	cluster	na	ya	nb	yb
1	1	5	1.782	0	6.239	0	3	0	1.697	0	5.942
1	2	2	1.239	2	4.337	0	4	1	1.533	0	5.368
1	6	3	2.508	2	8.779	0	5	1	1.273	1	4.456
1	8	2	2.390	2	8.365	0	7	1	1.057	1	3.699
1	10	2	2.373	1	8.306	0	9	0	2.737	0	9.582
1	12	2	2.863	2	10.023	0	11	1	1.701	0	5.955
1	13	1	1.909	0	6.684	0	15	1	1.142	0	3.997
1	14	1	1.134	0	3.971	0	16	2	1.646	1	5.763
1	19	1	1.675	1	5.865	0	17	1	2.110	1	7.385
1	21	1	2.949	0	10.324	0	18	0	2.751	0	9.631
1	23	3	2.452	4	8.585	0	20	0	1.409	0	4.932
1	24	1	1.090	1	3.817	0	22	7	2.785	4	9.749
1	27	3	2.491	0	8.721	0	25	0	2.168	0	7.591
1	28	2	1.992	0	6.972	0	26	1	1.739	0	6.088
1	30	0	2.433	0	8.517	0	29	5	2.701	9	9.454
1	31	0	2.719	0	9.518						

Stata code to estimate rate ratios RTS,S: comparator, and rate differences comparator-RTS,S:

```
* rate ratio:
svyset cluster
svy:ratio control: na/nb if area==0
scalar b0=_b[control]
scalar se0=_se[control]
scalar ndf0=e(df_r)
svy:ratio rtss: na/nb if area==1
scalar b1=_b[rtss]
scalar se1=_se[rtss]
scalar ndf1=e(df_r)
scalar se=sqrt(se0*se0/(b0*b0)+se1*se1/(b1*b1))
scalar b=log(b1)-log(b0)
scalar tval95=-invt(ndf0+ndf1,.025)
scalar tval99=-invt(ndf0+ndf1,.005)
di "Rate ratio:" exp(b),"95%CI:" exp(b-tval95*se),exp(b+tval95*se), ///
   "99%CI:" exp(b-tval99*se),exp(b+tval99*se)
* test of interaction:
scalar t=abs(b/se)
scalar p=ttail(ndf0+ndf1,t)*2
di t,ndf0+ndf1,p
* rate difference:
reshape long y,i(cluster) j(gp) str
encode gp,gen(ngp)
svy:ratio n/y if area==0,over(ngp)
lincom _b[a]-_b[b]
scalar d0=r(estimate)
scalar sed0=r(se)
scalar ndf0=r(df)
svy:ratio n/y if area==1,over(ngp)
lincom _b[a]-_b[b]
scalar d1=r(estimate)
scalar sed1=r(se)
scalar ndf1=r(df)
scalar rd=d0-d1
scalar serd=sqrt(sed0^2+sed1^2)
di "rate difference:" rd,"95%CI:" rd-tval95*serd,rd+tval95*serd, "99%CI:" ///
   rd-tval99*serd,rd+tval99*serd
```

Using the example data, this code gives the following estimates:

```
Rate ratio: 1.5650794 95%CI:0.61358341,3.992079
           99%CI:0.44306865,5.5284287
Interaction: t=0.97838205, 29df, P=0.3359772
Rate difference: -0.15947362 95%CI:-0.66267583,0.34372859
           99%CI:-0.8376466,0.51869936
```

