Annex 3: Summary of outcomes and analysis methods

[figure not shown]
Objectives	Outcomes	Methods	Timing	Analysis population
Impact: effect of RTS,S introduction on:				
All-cause mortality	Mortality (excluding injury)	Rate ratio and rate difference	When intermediate analysis is done (driven by accrual of safety outcomes), and at 46 months	A2
Severe malaria	Hospital admission with severe malaria	Rate ratio and rate difference (cases in hospital catchments)		A2
Secondary outcomes	Severe malaria anaemia; transfusions; all-cause admissions; malaria admissions; non-malaria admissions	Rate ratio and rate difference (cases in hospital catchments)		A2
Safety: effect of RTS,S introduction on rate of admission with:				
Meningitis	Hospital admission with probable meningitis	Rate ratio and rate difference (cases in hospital catchments)	When 80-100 cases have accrued in total in the 1-59 age group	A1
Cerebral malaria	Hospital admission with cerebral malaria	Rate ratio and rate difference (cases in hospital catchments)	to be defined	A1
Evidence of differential effect on mortality by gender	Mortality (all causes excluding injury)	Interaction by gender (comparison of proportion	When about 2000-2500 deaths (excluding injury) have accrued, among vaccine-eligible age groups	A1

boys and girls vaccinated,
among deaths in vaccine-
eligible age groups in RTS,S
clusters)

[figure not shown]
Objectives	Outcomes	Methods	Timing
Feasibility:			
Uptake of 3 doses by 12 mnths of age	Coverage of RTS,S doses 1,2,3	Ratio estimator (survey weighted); Kaplan Meier	When midline survey has been completed
Uptake of 4 doses by 27 mnths of age	Coverage of RTS,S doses 1,2,3,4	Ratio estimator (survey weighted); Kaplan Meier	When endline survey has been completed
Impact of RTS,S on EPI uptake	Coverage of penta-3 etc	Ratio estimator (survey weighted); Kaplan Meier	When midline survey has been completed
EPI data:			
Coverage of dose 4	Number of doses administered, by antigen and dose number	Descriptive	When intermediate analyses are done, and at month 46
Impact of RTS,S on EPI delivery	Number of doses administered, by antigen and dose number	Comparison of rates and drop-off rates between areas	

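### SAP Section 20 prints Cochran's Q with the variance where the standard error belongs; a one-line correction is needed

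*SAP*

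**What the plan says.** SAP Section 20, under Rate ratios, gives for each country a log rate ratio D = log(R1) - log(R0) with V(D) = V(R1)/R1^2 + V(R0)/R0^2. The three country values are pooled with weights 1/V(D_i). The confidence interval uses a t quantile times the square root of V(D_combined). The test for interaction by country is called Cochran's Q, carries a reference, and is the sum over countries of terms ending "D_{\text{combined}} - D_i)/V(D_i)]^2", referred to chi-square with 2 degrees of freedom.

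Section 19 says that incidence of the primary safety and impact outcomes will be compared between areas "in each country and for the three countries combined". Section 8 adds that, after a safety signal, "analysis will be done to determine if the results are similar in all three countries"; it names no test for this.

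The Annex 2 code handles one country. Its standard error is "scalar se=sqrt(se0*se0/(b0*b0)+se1*se1/(b1*b1"), and what it labels a test of interaction is the arm-by-age-group t test. It contains no pooling step and no Q.

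**The concern.** Cochran's Q weights each squared deviation by 1/V. The printed expression squares the whole fraction, so the weight becomes 1/V^2. The result depends on the scale of V. It is too large when V is below 1, which is the case for every outcome with many events, and too small when V is above 1.

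Impact is a primary objective overall and in each country, and this is the only formula the SAP gives for judging whether countries differ. An analyst who programs it as printed could report a consistent vaccine effect as differing between Ghana, Kenya and Malawi.

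**Working it through.** **Step 1. Is V(D) a variance? Reproduce Annex 2.** Applying the Section 20 formulas to the example data:
- RTS,S area: totals 29 (A) and 15 (B), R1 = 1.9333, V(R1) = 0.36198.
- Comparator area: totals 21 and 17, R0 = 1.2353, V(R0) = 0.17208.
- V(D) = 0.36198/1.9333^2 + 0.17208/1.2353^2 = 0.0968 + 0.1128 = 0.2096; square root 0.4578.
- D = ln(1.9333/1.2353) = 0.4479; D/0.4578 = 0.978.

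The rate ratio (1.5651), 95% interval (0.6136 to 3.9921) and t (0.978 on 29 df) match the printed values. V(D) is therefore a variance, and the SAP's own code divides by its square root.

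**Step 2. Effect of the printed form.** Correct: Q = sum of (D_i - D_combined)^2 / V_i. Printed: sum of (D_i - D_combined)^2 / V_i^2. With equal V, printed = Q/V. At the 5% cut-off of 5.991 its null rejection rate is P(chi-square on 2 df > 5.991 V) = exp(-2.996 V) = 0.05^V. This equals 5% only if V = 1.

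**Step 3. Size of V.** SAP Table 5 lists effect sizes under the column "Number of events required for given power to detect or exclude effects of the given size". Assuming a two-sided 5% test and a normal approximation, pooled V = (ln RR / 3.24)^2 at 90% power and (ln RR / 2.80)^2 at 80%. With information split equally, each country has three times the pooled V. As an alternative I used a 60/25/15 split, simulating 400,000 null triplets. For cerebral malaria at 400 events: (ln 2.03 / 3.24)^2 = 0.0477, times 3 = 0.143, and 0.05^0.143 = 0.65.

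| Outcome (ratio) | Events | V per country, equal split | Printed test rejects: equal split | 60/25/15 |
|---|---|---|---|---|
| Mortality (0.93) | 24,000 | 0.0015 | 99.6% | 99.4% |
| Mortality (0.90) | 17,600 | 0.0032 | 99.1% | 98.8% |
| Severe malaria (0.76) | 4,000 | 0.0215 | 94% | 92% |
| Severe malaria (0.76) | 3,000 | 0.029 | 92% | 90% |
| Cerebral malaria (2.03) | 400 | 0.143 | 65% | 58% |
| Cerebral malaria (2.03) | 300 | 0.192 | 56% | 49% |
| Meningitis (5.66) | 90 | 0.86 | 8% | 5% |
| Meningitis (5.66) | 70 | 1.15 | 3% | 2% |

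Two further planning figures fall within or near these ranges. For month 24, Section 8 expects "at least 80% power to detect a 2-fold increase in incidence of hospital admission with cerebral malaria": V = 3 x (ln 2 / 2.80)^2 = 0.184, and rejection is 58% (equal) or 50% (60/25/15). Annex 4's 5-fold meningitis case at 90% power gives V = 0.74, and rejection is 11% or 7%. The correct form rejected in 5% of simulations in every row.

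**Step 4. Two examples, equal V.**
- Cerebral malaria, 400 events, country ratios 1.5, 2.0, 2.7: the squared deviations of the logs sum to 0.1728. Correct Q = 0.1728/0.143 = 1.21, P = 0.55. Printed = 0.1728/0.143^2 = 8.4, P = 0.015.
- Severe malaria, 4,000 events, ratios 0.73, 0.76, 0.79: the sum is 0.00312. Correct Q = 0.145, P = 0.93. Printed = 6.7, P = 0.034.

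**Step 5. Sensitivity.** V can instead be taken from counts. Four equal totals of N/4 give pooled V = 16/N, multiplied by 2 or 4 for clustering. Allowing also a country with only 10% of the information, and the counts for both 80% and 90% power, rejection runs from 94% to 99.6% for mortality, 77% to 96.5% for severe malaria, 12% to 70% for cerebral malaria, and near 0% to 20% for meningitis. The direction holds for the first three outcomes; meningitis can go either way.

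**The case against.** The strongest reply is that the intent is clear. The test is named and referenced, the degrees of freedom are right, V is used correctly everywhere else in Section 20, and the only test the SAP codes divides by a standard error. Anyone using a packaged routine gets the right answer. This stands: the rejection rates above apply only if the formula is programmed literally. It does not remove the point, because nothing in the SAP corrects the formula and Annex 2 stops before the country step.

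A second reply is that a root over V(D_i) may have been lost when the PDF was converted to text. Squaring the whole bracket would be natural if the denominator had been a square root. Roots do survive in the confidence-interval formulas of Section 20, which makes this less likely but does not exclude it.

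A reader might also infer three stronger things that the documents do not support:
- **That the pooled result or a decision is at risk.** The pooled ratio and its interval do not use Q, and the SAP makes neither pooling nor any action conditional on it.
- **That the country check after a safety signal would use this statistic.** Section 8 names no test, so the link is only an inference.
- **That the error would pass unnoticed for cerebral malaria.** Its printed P-values can look plausible, but the same formula serves mortality. There a P-value below 1e-10 needs a printed statistic above 46.05, which under no country difference has probability exp(-23.03 V): 93-97% at the V of 0.0032 and 0.0015 above. Output that absurd would probably expose the mistake for all outcomes. The primary analysis of cerebral malaria is in any case pooled.

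**Conclusion.** As printed, the statistic is not Cochran's Q, and its reference distribution is wrong unless every V(D_i) equals 1. Coded literally, it would report a country difference where none exists in about 99% of data sets for mortality, 90-94% for severe malaria, 49-65% for cerebral malaria and 2-11% for meningitis, against 5% for the correct form. These figures rest on variances inferred from Table 5 (and Annex 4 for the 5-fold meningitis case), an assumed 5% level (the SAP states none for this test), and equal or 60/25/15 information splits that the documents do not give.

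The severity is minor. The intended method is identifiable, the effect estimates are untouched, and the harm is confined to how consistency between countries would be reported. That the plan itself contains the error is probable rather than certain until the original PDF is checked.

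**What to change.** Check the formula in the original SAP. If the root is absent there, replace it with Q = sum over the three countries of (D_i - D_combined)^2 / V(D_i), referred to chi-square with 2 degrees of freedom. The cost is one corrected line. Data collection, the pooled estimate, its confidence interval and the timing of analyses do not change.
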